6.4.11 SCHEDULE OF EVENTS TABLE

Schedule of Events	Phone Screen	Entry (Day 1)	Day 4	Day 10	Day 21
Review COVID-19 symptoms and date of COVID-19 testing; Obtain Demographics, verbal Ht and Wt and Co-Morbid Medical History; Obtain Verbal Informed Consent	x				
Update current illness and confirm eligibility for study; verify signing of Informed Consent		x			
Complete Symptom Scale and Clinical Status		x	x	x	x
Vital Signs (Temp, Pulse, BP, Resp Rate, O ₂ sat)		x	x	x	x
Pregnancy test (except in post-menopausal state)		x	x*	x*	x*
Oro-pharyngeal Swab		x	x	x	x
Safety Labs (CBC with diff, chem, hsCRP, LDH) [10 ml]		x	x	x	x
RESEARCH Bloods including for RAS assessment (volume to be drawn) [25 ml]		x	x	x	x
TOTAL BLOOD VOLUME (ml)		35	35	35	35

*If possibility of pregnancy is solicited from participant

6.5 CONCOMITANT MEDICATIONS, TREATMENTS, AND PROCEDURES

The participant's 'usual medications' may be continued unless specifically contra-indicated in this study. Antipyretics and other symptomatic medications and treatments will be allowed although participants will be asked to use judiciously and in moderation. The participant will be asked to call the Study Team if/when antibiotics or other medications are prescribed by the participant's own physician. In general these will be allowed except if drug-drug interaction with Telmisartan or if increased toxicity is of concern.

6.6 PROHIBITED OR PRECAUTIONARY MEDICATIONS, TREATMENTS, AND PROCEDURES

Use of ARBs (other than Telmisartan/Placebo being provided by the Study), ACE Inhibitors, Aliskiren, eplerenone, triamterene, amiloride, spironolactone and potassium supplements are prohibited.

6.7 PARTICIPANT ACCESS TO STUDY AGENT AT STUDY CLOSURE

Telmisartan will not be provided to any person outside the context of the study or following the closure of the study.

7 ASSESSMENT OF SAFETY

7.1 SPECIFICATION OF SAFETY PARAMETERS

7.1.1 DEFINITION OF ADVERSE EVENTS(AE)

Adverse event (AE) means any untoward medical occurrence associated with the use of an intervention in humans, whether or not considered intervention-related [21 CFR 312.32 (a)].

An AE can be any unfavorable and unintended sign (including an abnormal laboratory finding), symptom, or disease (new or exacerbated) temporally associated with the use of a study drug.

Collection of AEs will begin at the start of the study drug infusion and continue until the Final Visit.

AEs may be volunteered spontaneously by the subject or discovered as a result of general questioning by the study staff, by physical examination, or through procedures or laboratory testing. At each evaluation, the subject will be asked, "Have you experienced any problems or changes in your health since the last evaluation?" In addition, open-ended queries will help elicit information about possible AEs. All AEs will be recorded on the source documents and subsequently the CRF. For all AEs, the PI or Sub-I must pursue and obtain information adequate to determine the outcome of the AE and to assess whether it meets the criteria for classification as a serious AE requiring immediate notification. Follow-up of the AE is required until the event resolves, the condition stabilizes, the event is otherwise explained, or the subject is lost to follow-up.

To avoid vague, ambiguous, or colloquial expressions, all AEs should be recorded in standard medical terminology on the CRF and on the medical record rather than in the subject's own words. Each AE will also be described in terms of duration, frequency, severity, association with the study drug, assessment of possible causes, actions taken, and outcome, using choices given on the CRF. Specific guidelines for PI or Sub-I classification of AEs by severity and relationship to study drug are given below.

The toxicity grading system that will be used to grade the AE is the Division of AIDS Table for Grading the Severity of Adult and Pediatric Adverse Events, Version 2.0, November 2014, located at:
<https://rsc.tech-res.com/docs/default-source/safety/daids-aegrading-table-v2-nov2014.pdf>

7.1.2 DEFINITION OF SERIOUS ADVERSE EVENTS (SAE)

Serious adverse event or serious suspected adverse reaction (SAE) is an AE or suspected adverse reaction that is considered "serious" if, in the view of either the PI or Sub-I, it results in any of the following outcomes: death, a life-threatening adverse event, inpatient hospitalization or prolongation of existing hospitalization, a persistent or significant incapacity or substantial disruption of the ability to conduct normal life functions, or a congenital anomaly/birth defect. Important medical events that may not result in death, be life-threatening, or require hospitalization may be considered serious when, based upon appropriate medical judgment, they may jeopardize the patient or subject and may require medical or surgical intervention to prevent one of the outcomes listed in this definition. Examples of such medical events include allergic bronchospasm requiring intensive treatment in an emergency room or at home, blood dyscrasias or convulsions that do not result in inpatient hospitalization, or the development of drug dependency or drug abuse.

7.1.3 DEFINITION OF UNANTICIPATED PROBLEMS (UP)

OHRP considers unanticipated problems (UP) involving risks to participants or others to include, in general, any incident, experience, or outcome that meets all of the following criteria:

- Unexpected in terms of nature, severity, or frequency given (a) the research procedures that are described in the protocol-related documents, such as the IRB-approved research protocol and informed consent document; and (b) the characteristics of the participant population being studied.
- Related or possibly related to participation in the research (“possibly related” means there is a reasonable possibility that the incident, experience, or outcome may have been caused by the procedures involved in the research); and
- Suggests that the research places participants or others at a greater risk of harm (including physical, psychological, economic, or social harm) than was previously known or recognized.

This study will use the OHRP definition of UP.

7.2 CLASSIFICATION OF AN ADVERSE EVENT

7.2.1 SEVERITY OF EVENT

The following guidelines will be used to describe AE severity.

- **Mild (Grade 1)** – An event that is easily tolerated by the subject, causing minimal discomfort, and not interfering with everyday activities.
- **Moderate (Grade 2)** – An event that is sufficiently discomforting to interfere with normal everyday activities.
- **Severe (Grade 3)** – An event that prevents normal everyday activities.
- **Life-Threatening (Grade 4)** - An event that causes extreme limitation in activity or an event where significant medical intervention/therapy is required.
- **Death Related to AE (Grade 5)**- An event that results in a fatal outcome.

7.2.2 RELATIONSHIP TO STUDY AGENT

For all collected AEs, the PI or Sub-I who examines and evaluates the participant will determine the AE's causality based on temporal relationship and his/her clinical judgment. The degree of certainty about causality will be graded using the categories below.

- **Definitely Related**– There is clear evidence to suggest a causal relationship, and other possible contributing factors can be ruled out. The clinical event, including an abnormal laboratory test result, occurs in a plausible time relationship to drug administration and cannot be explained by concurrent disease or other drugs or chemicals. The response to withdrawal of the drug (dechallenge) should be clinically plausible. The event must be pharmacologically or phenomenologically definitive, with use of a satisfactory rechallenge procedure if necessary.
- **Probably Related** – There is evidence to suggest a causal relationship, and the influence of other factors is unlikely. The clinical event, including an abnormal laboratory test result, occurs within a reasonable time after administration of the drug, is unlikely to be attributed to concurrent disease or other drugs or chemicals, and follows a clinically reasonable response on withdrawal (dechallenge). Rechallenge information is not required to fulfill this definition.
- **Possibly Related** – There is some evidence to suggest a causal relationship (e.g., the event occurred within a reasonable time after administration of the trial medication). However,

other factors may have contributed to the event (e.g., the participant's clinical condition, other concomitant events). Although an AE may rate only as "possibly related" soon after discovery, it can be flagged as requiring more information and later be upgraded to "probably related" or "definitely related," as appropriate.

- **Unlikely to be related** – A clinical event, including an abnormal laboratory test result, whose temporal relationship to drug administration makes a causal relationship improbable (e.g., the event did not occur within a reasonable time after administration of the trial medication) and in which other drugs or chemicals or underlying disease provides plausible explanations (e.g., the participant's clinical condition, other concomitant treatments).
- **Not Related** – The AE is completely independent of study drug administration, and/or evidence exists that the event is definitely related to another etiology. There must be an alternative, definitive etiology documented by the clinician.

7.2.3 EXPECTEDNESS

[name] and Sub-Investigator will be responsible for determining whether an AE is expected or unexpected. An AE will be considered unexpected if the nature, severity, or frequency of the event is not consistent with the risk information previously described for the study agent.

7.3 TIME PERIOD AND FREQUENCY FOR EVENT ASSESSMENT AND FOLLOW-UP

The occurrence of an AE or SAE may come to the attention of study personnel during study visits and interviews of a study participant presenting for medical care. During each study visit or phone call, research nurse coordinator, PI, or Sub-I will query the participant for unsolicited and solicited AEs. All AEs including local and systemic reactions not meeting the criteria for SAEs will be captured on the appropriate CRF. Information to be collected includes event description, time of onset, clinician's assessment of severity, relationship to study product (assessed only by those with the training and authority to make a diagnosis), and time of resolution/stabilization of the event. All AEs occurring while on study must be documented appropriately regardless of relationship. All AEs will be followed to adequate resolution.

Any medical condition that is present at the time that the participant is screened will be considered as baseline and not reported as an AE. However, if the study participant's condition deteriorates at any time during the study, it will be recorded as an AE. UPs will be recorded in the CRF throughout the study.

Changes in the severity of an AE will be documented to allow an assessment of the duration of the event at each level of severity to be performed. AEs characterized as intermittent require documentation of onset and duration of each episode.

The PI or Sub-I will record all reportable events with start dates occurring any time after informed consent is obtained until 7 days for non-serious AEs and 30 days for SAEs after the last day of study participation. At each study visit, the investigator will inquire about the occurrence of AE/SAEs since the last visit. Events will be followed for outcome information until resolution or stabilization.

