SYMPTOM SCALE For each symptom below, please circle and grade how bad the symptoms were from Grade 0 (None, 0 point) to Grade 4 (Severe, 4 points):	Grade 0 (No symptom) (0 point)	Grade 1 (Mild symptom) (1 point)	Grade 2 (Moderate symptom) (2 point)	Grade 3 (Moderately severe symptom) (3 points)	Grade 4 (Severe symptom) (4 points)
FEVER In the previous 24 hours, my highest temperature was	Less than 100.4° (=No fever)	100.4° to 101.4°	101.5° to 102.6°	102.7° to 103.9°	104° or above
BREATHING I am short of breath -	None of the time	A little of the time (only when doing things that require extra effort like cleaning the house or walking rapidly or uphill)	Some of the time (I have to stop for breath when walking at my own pace)	Most of the time (I have to stop for breath when speaking)	All the time (even at rest when doing nothing)
FATIGUE I have -	No fatigue	A little bit of fatigue but it does not prevent me from doing the things I usually do	Some fatigue which is preventing me from doing some of the things I usually do	Moderate fatigue which is preventing me from doing most of the things I usually do	Severe fatigue I cannot take care of myself (dressing, taking a shower, brushing my teeth)

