4.1.2 SECONDARY ENDPOINT

- Number of grade II or higher adverse events (AE) through day 21 of study
- Levels of various components of the RAS system including Ang(1-12), AngI, AngII and Ang(1-7)
- Levels of various blood biomarkers

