9.3.3 ANALYSIS OF THE SECONDARY ENDPOINT(S)

Secondary efficacy endpoints for the study are given by a set of continuous/count measures observed at days 4, 10 and 21 (i.e., components of the RAS and blood biomarkers indicative of pro-inflammatory and coagulation disturbances, circulating T cell (CD4 and CD8), NK cell, and monocytes). A shift in distribution location parameter will be tested for the group companion, using two sample t-test or the Wilcoxon rank-sum test selected upon the outcome distributions. Additionally, longitudinal secondary outcomes obtained at baseline (day 1), days 4, 10, and 21 will be analyzed using generalized mixed effect models and together with a proper link function (i.e., identity, log, etc.). In those models, days: treatment interactions, will be tested for the differences in trajectories. Covariate adjustments will be applied if required.

AEs are categorical data. AEs will be summarized as frequencies and percentages within telmisartan and placebo groups. Chi-squared test or Fisher's exact test will be used to test for differences in proportions between two groups.

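### Worsening COVID-19 counts as an adverse event, so the grade II or higher AE endpoint partly overlaps the efficacy endpoint; report it with and without disease progression

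*Combined protocol and SAP*

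**What the plan says.** Section 7.3 sets the baseline: "Any medical condition that is present at the time that the participant is screened will be considered as baseline and not reported as an AE". The next sentence reads: "However, if the study participant's condition deteriorates at any time during the study, it will be recorded as an AE". The definition in 7.1.1 reaches any unfavourable "symptom, or disease (new or exacerbated) temporally associated with the use of a study drug", and 7.3 applies no causality filter: "All AEs occurring while on study must be documented appropriately regardless of relationship". None of these provisions exempts COVID-19. Under 7.1.2, death and inpatient admission make an event serious.

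The secondary safety endpoint in 4.1.2 is "Number of grade II or higher adverse events (AE) through day 21 of study". The primary endpoint in 4.1.1 is each participant's maximum Clinical Status. Scores 3.0 to 6.0 are hospitalized states, 7.0 is death, and the scores from 2.0 to 2.75 are set by a daily Symptom Scale for fever, breathing and fatigue.

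On analysis, 9.3.3 says "AEs will be summarized as frequencies and percentages within telmisartan and placebo groups", followed by chi-squared or Fisher tests of proportions. Section 9.3.4 tabulates events by grade and by symptom or laboratory parameter, with exact 95% intervals. Section 7.2.2 has the investigator grade causality for each event, but no analysis in 9.3.3 or 9.3.4 uses that grading or separates disease progression from other events.

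**The concern.** The second objective is the safety and tolerability of telmisartan. If worsening COVID-19 enters the AE count, benefit and toxicity move the same number in opposite directions. A drug that prevents admissions removes events from its own arm, and drug-caused events can then be added before the two totals differ. With no benefit, the COVID-19 events only add noise. If the drug worsened the illness, they would inflate apparent toxicity. In none of these cases does the total by itself describe tolerability.

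The count is also sensitive to how events are entered. Section 7.4.1 records changes of severity over several days separately, so one worsening illness can contribute several entries.

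**Working it through.** **1. The definitions side by side.** A grade 2 AE in 7.2.1 is "An event that is sufficiently discomforting to interfere with normal everyday activities". Grade 2 fatigue on the Symptom Scale is "Some fatigue which is preventing me from doing some of the things I usually do". For fatigue, a worsening to grade 2 therefore meets both thresholds. Every COVID-19 admission or death is both a serious event (7.1.2) and a Clinical Status of 3.0 or more (4.1.1).

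The overlap is not complete. Symptoms that persist at their baseline level count toward maximum severity from day 3, but they are not AEs under 7.3.

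**2. Reproducing the scenario in 9.4.** Placebo probabilities are 0.40, 0.40, 0.05, 0.04, 0.04, 0.04, 0.03. The telmisartan vector has six entries for seven categories (0.76, 0.18, 0.02, 0.01, 0.01, 0.01) and sums to 0.99.
- Odds ratio at the first cut: (0.76/0.24)/(0.40/0.60) = 4.75, close to the stated 5.0.
- Whitehead's formula with the telmisartan vector rebuilt at OR 5.0: V = 40 × (1 − 0.225)/12 = 2.58. One-sided 5% power = Φ(1.609 × 1.608 − 1.645) = 0.83.
- Simulation of the tie-corrected Wilcoxon score test (40,000 runs) gives 0.80 one-sided and 0.69 two-sided.

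The stated power of about 80% is thus reproduced with the one-sided test of 9.3.2.

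**3. Admissions and deaths (categories 3 to 7), 20 per arm.**
- Placebo: 0.05 + 0.04 + 0.04 + 0.04 + 0.03 = 0.20, × 20 = 4.0.
- Telmisartan as printed: 0.02 + 0.01 + 0.01 + 0.01 = 0.05, × 20 = 1.0. Completed to 1: 1 − 0.76 − 0.18 = 0.06, × 20 = 1.2.
- Telmisartan at exactly OR 5.0: odds 0.25/5 = 0.05, probability 0.05/1.05 = 0.048, × 20 = 0.95.
- Difference: 2.8 to 3.0 participants.

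The same calculation at smaller effects gives a difference of 2.5 at OR 3, 1.8 at OR 2 and 1.1 at OR 1.5.

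**4. Symptom worsening (assumption).** If 25% to 100% of category 2 participants also had a grade 2 deterioration, the difference at OR 5.0 would be:
- 25%: 20 × [(0.20 + 0.25 × 0.40) − (0.048 + 0.25 × 0.183)] = 4.1.
- 100%: 20 × [(0.20 + 0.40) − (0.048 + 0.183)] = 7.4.

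The documents do not say where in that range the truth lies.

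**5. How much toxicity this could offset.** Assume each admission or death is one AE participant, drug events are independent of progression, and b is the background risk of other AEs. The arms have equal participant-level rates when the telmisartan non-COVID risk is q = [0.20 + 0.80b − h]/(1 − h), with h = 0.048 to 0.06.
- b = 0: q = 0.149 to 0.160, an excess of 15 to 16 points.
- b = 0.20: q = 0.319 to 0.328, an excess of 12 to 13 points.

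**6. What separation would recover (two-sided Fisher, 20 per arm).** These toxicity rates are assumed, and the comparison uses OR 5.0.
- 15% v 0%, no background: power 17% with progression kept apart, 1% pooled.
- 30% v 0%, no background: 76% apart, 9% pooled (33% v 20%).
- 30-point excess on a 10% background: 49% apart, 10% pooled.

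An observed 3 of 20 v 0 of 20 gives p = 2 × C(20,3)/C(40,3) = 2 × 1140/9880 = 0.23.

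**The case against.** A reader might infer that the plan hides drug toxicity. The documents do not support that. The table in 9.3.4 would put hypotension, potassium or creatinine events on their own rows, 9.3.10 lists individual data, and 7.6.1 has safety laboratory results reviewed within 24 hours. Only the total, or a test of it, can be distorted.

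Nor does 9.3.3 clearly say that one pooled total is tested. Its wording also fits tests by event category. It is simply unspecific.

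The size can be questioned too. The OR 5.0 scenario is introduced as a supposition. The toxicity rates above are not from the plan: in 2.2.1 the listed telmisartan excesses are 1 to 2 points and overall incidence is similar to placebo, though in a different population. At 15% toxicity the separated comparison would usually miss the signal as well.

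The symptom overlap has limits. Participants who qualify through fatigue already have more than minimal interference (5.1), so much of that is baseline. Sections 6.1.7 and 7.1.1 also name an external grading table that is not reproduced, so no grade match can be shown for fever or breathing.

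Finally, an all-cause comparison needs no attribution. Excluding fatigue or respiratory events could remove some that the drug caused.

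All of this stands, and it limits the point. It leaves the main fact untouched: the endpoint as defined counts progression of the enrolled illness, and no planned analysis separates it.

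**Conclusion.** The point holds in a limited form and is minor. The AE count in 4.1.2 partly overlaps the primary endpoint because 7.1.1 and 7.3 record worsening COVID-19 and 7.1.2 covers admission and death. At the plan's own OR 5.0, this alone gives about 3 fewer AE participants per 20 on telmisartan, falling to about 1 at OR 1.5. It rests on each admission or death being recorded as a grade II or higher AE by day 21. Masking further requires a real benefit and reliance on the total or a pooled test.

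Two stronger readings should be resisted. The endpoint does not contain the whole efficacy outcome, since persisting baseline symptoms are not AEs. And the figures do not show that a particular toxicity would be missed because of pooling, since no AE rate for this population is given. The trial is a 40-person pilot sized on feasibility, and neither 7.5 nor 9.3.7 ties a safety decision to the AE total.

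**What to change.** In 4.1.2, 9.3.3 and 9.3.4:
- Keep the all-cause grade II or higher AE count and its between-arm comparison.
- Pre-specify beside it the same comparison excluding COVID-19 progression, defined as worsening fever, dyspnoea or fatigue judged due to COVID-19, and COVID-19 admission or death.
- Have the PI or Sub-I flag these events on the CRF before unblinding.
- Report participants with at least one event as well as the number of events.

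SAE reporting is unchanged.

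The cost is one CRF field and a few table rows. The downside is a blinded attribution judgement that may misclassify some drug-caused fatigue or respiratory events, which is why the all-cause count stays alongside. The same investigators already grade causality under 7.2.2.

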7.4 REPORTING PROCEDURES

7.4.1 ADVERSE EVENT REPORTING

All AEs will be recorded on the source documents and subsequently the CRF. For all AEs, the PI or Sub-I must pursue and obtain information adequate to determine the outcome of the AE and to assess

whether it meets the criteria for classification as a serious AE requiring immediate notification. Follow-up of the AE is required until the event resolves, the condition stabilizes, the event is otherwise explained, or the subject is lost to follow-up.

To avoid vague, ambiguous, or colloquial expressions, all AEs should be recorded in standard medical terminology on the CRF and on the medical record rather than in the subject's own words. Each AE will also be described in terms of duration, frequency, severity, association with the study drug, assessment of possible causes, actions taken, and outcome, using choices given on the CRF. Specific guidelines for Investigator classification of AEs by severity and relationship to study drug outlined in [Sections 7.2.1, 7.2.2, 7.2.3](#) and [7.3](#).

When changes in the severity of an AE occur more frequently than once a day, the maximum severity for the experience that day should be noted. If the severity category changes over a number of days, then those changes will be recorded separately (with distinct onset dates).

AE will be reported to the IRB. The PI or designee is responsible for assessing each event and signing off on the AE report.

